**Table 10–1: Vital Signs Abnormality Criteria**

Parameter	Age Range	Abnormality Criteria
Pulse Rate (beats/minute)	4y - <12y	<60 >130
	12y - <17y	≤50 ≥120
	≥17y	≤50 and a decrease from Baseline of ≥15 ≥120 and an increase from Baseline of ≥15
Systolic Blood Pressure (mmHg)	4y - <12y	<80 >140
	12y - <17y	<90 >160
	≥17y	≤90 and a decrease from Baseline of ≥20 ≥180 and an increase from Baseline of ≥20
Diastolic Blood Pressure (mmHg)	4y - <12y	<50 >80
	12y - <17y	≤50 ≥105
	≥17y	≤50 and a decrease from Baseline of ≥15 ≥105 and an increase from Baseline of ≥15
Respiratory Rate (breaths/minute)	4y - <12y	<15 >35
	≥12y	<10 >25
Temperature	All	>101 °F (38.3 °C)
Body Weight	4y - <17y	<3% or >97% of the normal body weight growth curve ranges a based on gender and the age of subject on date of weight assessment
	≥17y	≥10% change from Baseline (an increase or a decrease)

Abbreviations: m = month, y = year. A month is defined as 30 days; a year is defined as 365.25 days.

Additionally, a subject will be considered to have marked bradycardia if the pulse rate is <45bpm and an AE mapped to the PT bradycardia is reported for the subject. A listing of vital signs data

will be provided for all subjects with marked bradycardia. Additionally, a subject data listing of all vital signs for subjects with an AE mapped to the PT bradycardia will be presented.

A subject data listing of all vital signs values including body weight, height, BMI, and head circumference for all subjects will be presented. A separate listing including TEMA vital signs values will also be presented.

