4.2.2 Other safety variables

- Changes in hematology, clinical chemistry, and endocrinology parameters
- Changes in 12-lead ECGs
- Changes in vital sign measurements (ie, blood pressure [BP] and pulse rate)
- Physical and neurological examination findings
- Changes in body weight, height, and calculated body mass index
- Behavioral assessments (Achenbach CBCL/1½-5 or CBCL/6-18)
- Cognitive function assessments (BRIEF-P/BRIEF)

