6 SELECTION AND WITHDRAWAL OF SUBJECTS

6.1 Inclusion criteria

To be eligible to participate in this study, all of the following criteria must be met:

1. An Institutional Review Board (IRB)/Independent Ethics Committee (IEC) approved written Informed Consent form is signed and dated by the parent(s) or legal representative. The Informed Consent form or a specific Assent form, where required, will be signed and dated by minors.
2. Subject/legal representative is considered reliable and capable of adhering to the protocol (eg, able to understand and complete diaries), visit schedule, and medication intake according to the judgment of the investigator.
3. Subject is male or female from ≥ 4 years to < 17 years of age.
4. Subject has a diagnosis of epilepsy with partial-onset seizures. The results of ≥ 1 prior electroencephalogram (EEG) AND 1 prior magnetic resonance imaging/computerized tomography scan should be consistent with the above diagnosis.
5. Subject has been observed to have uncontrolled partial-onset seizures after an adequate course of treatment (in the opinion of the investigator) with ≥ 2 AEDs (concurrently or sequentially).
6. Subject must have been observed to have on average ≥ 2 partial-onset seizures per 28 days with seizure-free phase no longer than 21 days in the 8-week period prior to entry into the Baseline Period. During this study, subjects must have reported ≥ 2 partial-onset seizures during the 8-week prospective Baseline Period to be eligible for randomization at Visit 2. (Note: In the case of simple partial-onset seizures, only those seizures with motor signs will be counted towards meeting the inclusion criterion.)
7. Subject is on a stable dosage regimen of 1 to ≤ 3 AEDs. The daily dosage regimen of concomitant AED therapy must be kept constant for a period of ≥ 4 weeks prior to the Baseline Period.
8. Vagal nerve stimulation is allowed and will not be counted as a concomitant AED. The VNS device must be implanted for ≥ 6 months before Visit 1, and the device settings must be stable for ≥ 4 weeks before Visit 1 and be kept stable during the Baseline Period. Use of the VNS device magnet is allowed.

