## **10.4 Vital signs, physical findings, and other observations related to safety**

### **10.4.1 Vital signs, body weight, height, BMI, and head circumference**

Vital signs (systolic BP [SBP], diastolic BP [DBP], and pulse rate) will be assessed after at least 3 minutes at rest in a supine position throughout the study from Visit 1 (entry to study) to Visit 8, and at ETV in case of early termination, and at unscheduled visits. Vital signs will also be assessed during the Transition Period, Taper Period, and at the Safety Follow-Up Visit.

Assessment of orthostatic changes will also be performed as follows: After the 3 minute measurement in supine position, the subject is asked to stand up, and SBP, DBP and pulse rate are taken approximately 1 minute and approximately 3 minutes after the subject stands up as feasible.

Body weight will be assessed throughout the study from Visit 1 (entry to study) to Visit 8, and at ETV in case of early termination, and at unscheduled visits. Body weight will also be assessed during the Transition Period, Taper Period, and at the Safety Follow-Up Visit.

Height will be assessed at Visit 1 (entry to study), Visit 2 (Baseline), Visit 8, and at ETV in case of early termination. BMI will subsequently be calculated at these visits.

Head circumference will be assessed at Visit 1 (entry to study), Visit 8, and at ETV in case of early termination.

Observed values of SBP, DBP, pulse rate, body weight, height, BMI, and head circumference will be summarized by treatment group for each visit and Last Visit. Change from Baseline for SBP, DBP, pulse rate, body weight, height, BMI and head circumference will be summarized by treatment group for all post-Baseline visits, and Last Visit, as appropriate.

Orthostatic changes of SBP, DBP, and pulse rate will be summarized by treatment group for each visit and Last Visit.

Markedly abnormal (MA) values are defined as those MA values which occur during the defined Treatment Period (see Section 3.2.2) at scheduled or unscheduled visits on or after the first study medication administration through to the end of the Treatment Period.

The number and percentage of subjects with a MA value, MA low value, and MA high value, at each post-Baseline visit up to Visit 8, for which SBP, DBP, pulse rate, and body weight were

scheduled to be assessed, and Last Visit, will be presented. Percentages will be relative to the number of subjects with a value at each visit.

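### For subjects under 17, SAP Table 10-1 judges body weight by a fixed percentile limit only, so no planned output counts marked relative weight change by arm

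*SAP*

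**What the plan says.** Protocol section 4.2.2 names "Changes in body weight, height, and calculated body mass index" among the other safety variables, and SAP section 2.2.2.2 repeats it. Protocol section 6.1 sets the age range: "Subject is male or female from ≥ 4 years to < 17 years of age".

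SAP Table 10-1 (section 10.4.1) has two body-weight rows:

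- **4 to under 17 years:** a value is abnormal if it is "<3% or >97% of the normal body weight growth curve ranges", "based on gender and the age of subject on date of weight assessment". I read this as the 3rd and 97th percentiles.
- **17 years and over:** "≥10% change from Baseline (an increase or a decrease").

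Section 10.4.1 sets the counting window: "Markedly abnormal (MA) values are defined as those MA values which occur during the defined Treatment Period". It does not ask that the Baseline value be normal. It plans separate low and high counts for body weight at each visit up to Visit 8 and at Last Visit.

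Two other outputs carry weight. One is a group summary: "Change from Baseline for SBP, DBP, pulse rate, body weight, height, BMI and head circumference will be summarized by treatment group". The other is a listing: "A subject data listing of all vital signs values including body weight, height, BMI, and head circumference for all subjects will be presented".

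**The concern.** The declared variable is change in weight, but the criterion that covers almost every subject measures size. A percentile limit answers whether a child is small or large for age and sex, and that is mostly settled before the first dose. The row that does measure change is reserved for an age group that cannot be enrolled.

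At stake is one safety table. If a minority of children in one arm lost a marked share of their weight, the markedly abnormal count might not differ between arms. If the arms differed by chance in how many small or large children they enrolled, the count could differ with no change in weight. Relative loss also bears on reading exposure: dose is set on Visit 2 weight throughout, so at an unchanged dose a 10% loss raises the mg/kg actually received by a factor of 1/0.9 = 1.11.

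**Working it through.** The plan gives no figure of its own here, so there is nothing to reproduce. The check is of what the rule counts, followed by an illustration of scale.

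**1. Who the change-based row can reach.** Table 10-1 refers to age on the date of the weight assessment. If that age also selects the row, a subject who turns 17 on study moves to the 10% rule; if age at entry were used, nobody would. Assume ages uniform over the 13 years from 4 to under 17. There are 16 weeks from first dose to Visit 8, and 24 weeks from Visit 1 to Visit 8.

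- 16/52/13 = 2.4%
- 24/52/13 = 3.6%

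So about 2% to 4% of subjects could come under the change rule by Visit 8.

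**2. When a loss is counted under 17 (no distribution assumed).** Let W0 be Baseline weight, L the fraction lost, and P3 and P97 the limits at the assessment. The new weight W0 × (1 − L) counts as low only if it is below P3, that is, if W0 < P3/(1 − L). It counts as high only if it is still above P97. Otherwise it is not counted. On the low side:

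- L = 10%: not counted low once W0 ≥ 1.111 × P3
- L = 20%: not counted low once W0 ≥ 1.25 × P3

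**3. When no change is counted.** The definition in section 10.4.1 needs only a value outside the limits during the Treatment Period. A child below P3 or above P97 before dosing who stays there is counted. The ECG rule in SAP section 10.4.2 differs: to be treatment-emergent, an abnormality must not have been met at Baseline.

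**4. Scale (assumed spread; not in the documents).** Assume normal weight-for-age with coefficient of variation CV and limits unchanged over 16 weeks. The 3rd percentile is at z = −1.881. A median child must lose 1.881 × CV to reach it. After a 10% loss, the share still above P3 is P(Z > ((1 − 1.881 CV)/0.9 − 1)/CV). The share still above P97, which the table does count, is P(Z > ((1 + 1.881 CV)/0.9 − 1)/CV).

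| CV | Loss needed at median | Above P3 after 10% loss | Of these, still above P97 | Not counted |
|---|---|---|---|---|
| 12% | 22.6% | 87.8% | 0.1% | 87.6% |
| 15% | 28.2% | 91.1% | 0.2% | 90.9% |
| 20% | 37.6% | 93.8% | 0.4% | 93.3% |

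As a second model, take log-normal weight-for-age with log-SD s, restricted to children who start between P3 and P97. The starting z above which a 10% loss is not counted is −1.881 − ln(0.9)/s. The share not counted is (0.97 − Φ(that z))/0.94.

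| s | Starting z | Not counted after 10% loss | Median child falls to percentile |
|---|---|---|---|
| 0.12 | −1.00 | 86.4% | 19th |
| 0.15 | −1.18 | 90.5% | 24th |
| 0.20 | −1.35 | 93.8% | 30th |
| 0.25 | −1.46 | 95.5% | 34th |

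Both models agree: under any spread in these ranges, most children who lost 10% would not be counted.

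**5. Whether another output supplies the count.** SAP section 3.1 defines descriptive statistics as n, mean, SD, median, minimum and maximum, and section 10.4.1 specifies no percent change for weight. A 3 kg loss is 10% of 30 kg but 5% of 60 kg, so a minimum in kg neither identifies marked relative loss nor says how many subjects had it. The listings show each subject but attach no threshold. The weight-band subgroups in SAP section 4.8 are for exposure and adverse events, not for weight change.

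**The case against.** The strongest reply is that the loss does not go unseen. SAP section 3.1 promises listings that include calculated data such as change from Baseline, and section 10.4.1 lists every weight. The group summary carries the minimum, which is the largest loss in kg. Weight is measured at every clinic visit, and Protocol section 8.2 has the investigator weigh it when judging tolerability during titration. A clinically relevant loss could be reported as an adverse event and counted by arm there. All of this stands. A reader might infer from Table 10-1 that a child could lose 10% of body weight unnoticed; the documents do not support that. None of these routes, however, gives a threshold-based count by arm. The adverse event route depends on an investigator judging the loss worth reporting.

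A second reply is that the row follows a pattern. Pulse, systolic and diastolic pressure in the same table also use fixed limits under 17 and add change from Baseline only at 17 and over. This also stands: a reader might take the row for a slip carried over from adult criteria, and the table gives no ground for that. It does not show that a size limit suits a variable defined as change. SAP Table 10-2 already uses relative change from Baseline under 17, for example for QTc.

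Third, nothing in the documents suggests that weight loss is expected. Protocol section 2 reports that preliminary pediatric data gave no evidence of body weight changes, and weight is not a primary safety variable. This stands and keeps the priority low.

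**Conclusion.** The point holds in limited form. While a subject is under 17, a loss of 10% or more counts as markedly abnormal only if the new weight is below the 3rd percentile or still above the 97th, and a subject outside those limits at Baseline counts with no change. No planned output counts subjects with marked relative weight change by arm. These statements follow from the wording of the table and the counting definition, and need no distribution.

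The 88% to 94% figures are illustrative and rest on the assumed CV of 12% to 20%. They include the few children still above the 97th percentile, whom the table does count; removing them gives 87.6% to 93.3%. They describe children who hypothetically lose 10%. A reader might take them as the share of cases this trial would miss, but the documents say nothing about how many children would lose that much in 16 weeks. The 2% to 4% who could turn 17 rests on uniform ages.

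No efficacy result, sample size or primary safety variable depends on this row. It is a cheap improvement of low priority.

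**What to change.** In Table 10-1, apply the existing criterion of 10% or more change from Baseline to all ages, in addition to the percentile criterion. Report it as its own line within the low and high counts already planned, with decreases under low and increases under high, so that size and change are not merged. Note in the table or the SAP text that some gains of 10% or more will be normal growth and are to be read against placebo.

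The cost is one added table criterion and its output line. The weights are already collected at every clinic visit, and no new data or visits are needed. The one drawback is the normal-growth gains in the high count, for which the randomized placebo arm gives the reference.

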11.3 Adverse events of special interest

An AE of special interest is any AE that a regulatory authority has mandated be reported on an expedited basis, regardless of the seriousness, expectedness, or relatedness of the AE to the administration of a UCB product/compound.

The following are AEs of special interest:

- The following arrhythmias: atrial fibrillation/flutter, ventricular tachycardia or fibrillation, AV block (2nd degree Type I and II and 3rd degree), and marked bradycardia (<45bpm)
- Syncope or loss of consciousness (other than seizure related)
- Serious suspected multiorgan hypersensitivity reactions

Serious suspected multiorgan hypersensitivity cases may be identified and reported to the sponsor by the investigator using the following algorithm as agreed with the United States Food and Drug Administration:

An AE or laboratory value (as defined in the following text) suggestive of internal organ involvement (including but not limited to hepatitis, nephritis, pneumonitis, carditis, colitis, encephalitis, pancreatitis, myositis, arthritis, or hematologic system involvement) combined with at least 1 of the following: fever, rash, lymphadenopathy, or eosinophilia.

Treatment-emergent abnormal laboratory value criteria suggestive of internal organ involvement or eosinophilia:

- Eosinophils % $\geq 10\%$
- Eosinophils absolute $\geq 0.5\text{G/L}$
- Neutrophils absolute $< 1.5\text{G/L}$
- Platelets $\leq 100\text{G/L}$
- ALT $\geq 2 \times \text{ULN}$
- AST $\geq 2 \times \text{ULN}$

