The incidence of drug-related TEAEs by seriousness will be presented for each treatment group by MedDRA primary SOC and PT.

The incidence of TEAEs by dose at onset will be presented for each treatment group by MedDRA primary SOC and PT, and will be repeated by treatment group and age group, and by treatment group and weight group using the levels defined in section 4.8.

The incidence of non-serious TEAEs occurring in at least 5% of subjects in any treatment group will be summarized for each treatment group by MedDRA primary SOC and PT, and will be repeated by treatment group and age group, using the levels defined in section 4.8.

Other significant AEs, defined in Appendix 12 (section 12.2), will be summarized for each treatment group by MedDRA primary SOC and PT, and will be repeated by treatment group and weight group, using the levels defined in section 4.8.

In addition, summaries for the incidence of TEAEs overall, incidence of serious TEAEs, incidence of TEAEs leading to discontinuation of study medication, and incidence of other significant TEAEs will be repeated presenting the site and subject number of all those subjects experiencing each TEAE. Subject data listings will also be presented.

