## 12.2 Other significant adverse events

MedDRA Preferred Term
HEPATOTOXICITY RELATED TERMS
Hepatitis toxic
Hepatotoxicity
CARDIAC AND ECG RELATED TERMS
Atrioventricular block third degree
Atrioventricular block second degree
Bradycardia
Bradycardia
Cardiac pacemaker insertion
Atrial fibrillation
Atrial flutter
Sinus bradycardia
Ventricular tachycardia
Ventricular fibrillation
Heart Rate decreased
Sick sinus syndrome
SUICIDALITY RELATED TERMS
Completed suicide
Depression suicidal
Suicidal behavior
Suicidal ideation
Suicide attempt
Intentional self-injury
Self injurious behavior
Self-injurious ideation
Intentional overdose
Multiple drug overdose intentional
Poisoning deliberate
ADDITIONAL TERMS
Loss of consciousness
Syncope

This document cannot be used to support any marketing authorization application and any extensions or variations thereof.

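### SAP 10.4.1 ties marked bradycardia to one preferred term, so a pulse below 45 bpm with an AE coded to another slow-rate term falls outside the class and its listing

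*SAP*

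**What the plan says.** Protocol 11.3 names certain arrhythmias as adverse events of special interest. The last item in that group is "and marked bradycardia (<45bpm". The rate is given, but no MedDRA preferred term. The same section makes clear that the category consists of adverse events: "An AE of special interest is any AE that a regulatory authority has mandated be reported on an expedited basis".

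SAP 10.4.1, in the text after Table 10-1, turns this into an analysis rule: "a subject will be considered to have marked bradycardia if the pulse rate is <45bpm and an AE mapped to the PT bradycardia" has been recorded. The only output built on the rule is a listing of vital signs, which "will be provided for all subjects with marked bradycardia". A second listing covers every subject with an AE under the preferred term bradycardia, whatever the pulse.

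SAP 12.2 gives the sponsor's own list of other significant AEs. Its cardiac group contains Bradycardia (printed twice), "Sinus bradycardia" and "Heart Rate decreased". SAP 10.2 uses that list: "Other significant AEs, defined in Appendix 12 (section 12.2), will be summarized for each treatment group by MedDRA primary SOC and PT".

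**The concern.** The SAP rule is narrower than the protocol item it appears to implement, and narrower than the SAP's own list of slow-rate terms. Whether a child with a pulse below 45 bpm and a reported slow-rate event is classed as having marked bradycardia depends on which of several near-synonymous terms the verbatim was coded to. For an event the protocol singles out for special attention, a coding choice should not decide this.

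At stake is how the clinical study report describes one cardiac safety item. If the marked-bradycardia listing is read as the set of cases, it can be incomplete, and a reader of the planned tables could not recover the number of subjects below the protocol's threshold by treatment group.

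**Working it through.** No arithmetic figure is at issue, so the check sets the rule beside the protocol item, the term list and the other planned outputs.

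**1. Who is classed.** Take subjects with a pulse below 45 bpm.

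| Adverse event record | Meets the protocol rate and is an AE | Marked bradycardia under SAP 10.4.1 |
|---|---|---|
| Coded to Bradycardia | Yes | Yes |
| Coded to Sinus bradycardia | Yes | No |
| Coded to Heart Rate decreased | Yes | No |
| No AE recorded | Rate only; not by itself an event of special interest | No |

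Rows 2 and 3 are the gap. Of the three distinct slow-rate terms in SAP 12.2, one qualifies.

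**2. What the 45 bpm condition adds.** All subjects with the term bradycardia already have their vital signs listed at any pulse. The marked-bradycardia listing is therefore a subset of that listing and brings forward nobody whom the term alone would not.

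**3. Timing.** The rule requires only that the pulse value and the AE belong to the same subject. It sets no window and does not say that the pulse must be after the first dose. An unrelated pair could therefore be classed as a case.

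**4. Whether another output gives the below-45 figure.**

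- *Low pulse.* SAP 10.4.1 plans "The number and percentage of subjects with a MA value, MA low value, and MA high value" by visit, with no AE condition. The low-pulse limits in Table 10-1 are below 60 bpm for ages 4 to under 12 and 50 bpm or lower for ages 12 to under 17. Every Treatment Period pulse below 45 in those ages is included, but mixed with higher values. For a subject who has reached 17, a fall of at least 15 from Baseline is also required, so a pulse of 44 is flagged only if Baseline was at least 44 + 15 = 59.
- *ECG heart rate.* Table 10-2 uses below 60 bpm under age 12 and below 50 bpm from age 12. SAP 10.4.2 counts an abnormality as treatment-emergent only if the same criterion was not met at Baseline. A 13-year-old going from 48 to 42 bpm is therefore not counted.
- *AE summary.* The SAP 12.2 terms are tabulated by treatment group without any rate.
- *Period.* The low-pulse and ECG abnormality counts stop at the end of the Treatment Period. Under Protocol 7.2.3, placebo subjects first receive lacosamide in the Transition Period, and Protocol Table 5-2 schedules pulse at all four Transition visits. A value below 45 bpm there, or in the Taper Period, appears only in listings.

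None of these outputs applies the 45 bpm cut.

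**The case against.** The strongest reply is that little is hidden. Sinus bradycardia and Heart Rate decreased are summarized by treatment group and again by weight group, with subject numbers shown. SAP 10.4.2 lists ECG data for every subject with a cardiac term from SAP 12.2. All vital signs and all ECG values are listed for all subjects. Safety surveillance does not depend on the rule either: Protocol 11.4 requires immediate reporting of events of special interest, and SAP 4.3 has the SAP 12.2 events triaged in real time and passed to the data monitoring committee as appropriate. All of this stands, and it limits the point to how cases are classified and presented.

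A reader might go further and infer any of the following, which the documents do not support:

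- *Every pulse below 45 bpm without an AE is a missed event of special interest.* Protocol 11.3 defines these events as adverse events, so requiring an AE is consistent with it. A low reading alone is useful supporting information, since the AE definition in Protocol 11.1.1 extends to unfavorable signs, but it is not automatically a case.
- *Cases vanish from the report.* They are absent only from this class and its listing.
- *The SAP will publish too low a count.* It plans a listing under this rule, with no number or percentage.
- *The rule can only reduce the number of cases.* With no time link, an unrelated pulse and AE can also qualify.

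The reply does not explain why one term was chosen when the SAP's own list holds two others, and it supplies no output at 45 bpm.

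**Conclusion.** The point holds as a mismatch between Protocol 11.3, SAP 10.4.1 and SAP 12.2. A subject with a pulse below 45 bpm and an AE coded to Sinus bradycardia or Heart Rate decreased is not classed as having marked bradycardia, and no planned output isolates rates below 45 bpm by treatment group.

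The size in subjects is unknown. The documents give neither the expected frequency of such rates nor how slow-rate events are distributed across the terms; one qualifying term out of three describes the rule and is not an estimate of cases lost. The conclusion assumes that the SAP rule is meant to represent the protocol item, which the shared name and threshold suggest, and that at least some slow-rate events would be coded to the other two terms. It affects the completeness of one safety presentation. It does not touch the efficacy analysis, the detection of events during the trial, or any clinical rule.

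**What to change.** In SAP 10.4.1, define marked bradycardia as a pulse rate or 12-lead ECG heart rate below 45 bpm after the first dose, with a temporally associated AE coded to any slow-rate term in SAP 12.2 (Bradycardia, Sinus bradycardia, Heart Rate decreased). State the time window and cover scheduled and unscheduled values, including those in the Transition and Taper Periods. Check whether the second Bradycardia entry in SAP 12.2 was meant to be another term.

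Give the number of subjects by treatment group, and extend the listing to match. Show separately, as a supportive row, subjects with a rate below 45 bpm and no such AE, so that they are visible without being labelled events of special interest.

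The cost is a wording change, a revised listing and one extra row or small table from data already collected. The resulting figure may look less favourable, and the supportive row will include some isolated asymptomatic readings.
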